## Memorial Sloan-Kettering Cancer Center IRB Protocol

**IRB#: 08-123 A(8)**

### 9.3 Monitoring of Everolimus suspected toxicities

Patients whose treatment is interrupted or permanently discontinued due to an adverse event or an abnormal laboratory value suspected to be related to Everolimus must be followed at least weekly until the adverse event or abnormal laboratory value resolves or returns to grade 1. If a patient requires a dose delay of > 21 days from the intended day of the next scheduled dose, then the patient must be discontinued from the study.

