## Memorial Sloan-Kettering Cancer Center IRB Protocol

**IRB#: 08-123 A(8)**

**Table 4. Criteria for dose-modification in case of suspected Everolimus toxicity and re-initiation of Everolimus treatment**

Toxicity	Actions
Non-hematological toxicity	
Grade 2 (except pneumonitis – refer to Table 5)	If the toxicity is tolerable to the patient, maintain the same dose. If the toxicity is intolerable to patient, interrupt Everolimus until recovery to grade $\leq 1$ . Then reintroduce Everolimus at same dose. If event returns to grade 2, interrupt Everolimus until recovery to grade $\leq 1$ , then reintroduce Everolimus at the lower dose level.
Grade 3 (except hyperlipidemia*)(except pneumonitis – refer to Table 5)	Interrupt Everolimus until recovery to grade $\leq 1$ , then reintroduce Everolimus at the lower dose level. For pneumonitis consider the use of a short course of corticosteroids.
Grade 4 (including hyperlipidemia)	Discontinue Everolimus.
Hematological toxicity	
Grade 2 Thrombocytopenia (platelets $< 75, \geq 50 \times 10^9/L$ )	Interrupt Everolimus until recovery to grade $\leq 1$ ( $> 75 \times 10^9/L$ ), then reintroduce Everolimus at initial dose. If thrombocytopenia again returns to grade 2, interrupt Everolimus until recovery to grade $\leq 1$ . Then reintroduce Everolimus at the lower dose level.
Grade 3 Thrombocytopenia (platelets $< 50, \geq 25 \times 10^9/L$ )	Interrupt Everolimus until recovery to grade $\leq 1$ ( $\text{platelets} \geq 75 \times 10^9/L$ ). Then resume Everolimus at one dose level lower. If grade 3 thrombocytopenia recurs, discontinue Everolimus.
Grade 4 Thrombocytopenia (platelets $< 25 \times 10^9/L$ )	Discontinue Everolimus.
Grade 3 Neutropenia (neutrophils $< 1, \geq 0.5 \times 10^9/L$ )	Interrupt Everolimus until recovery to grade $\leq 1$ ( $\text{neutrophils} \geq 1.5 \times 10^9/L$ ), then resume Everolimus at the initial dose. If ANC again returns to Grade 3, hold Everolimus until the ANC $\geq 1.5 \times 10^9/L$ , then resume Everolimus dosing at the lower dose level. Discontinue patient from study therapy for a third episode of grade 3 neutropenia.
Grade 4 Neutropenia (neutrophils $< 0.5 \times 10^9/L$ )	Interrupt Everolimus until recovery to grade $\leq 1$ ( $\text{neutrophils} \geq 1.5 \times 10^9/L$ ). Then resume Everolimus at the lower dose level. If grade 3 or grade 4 neutropenia occurs despite this dose reduction, discontinue Everolimus.

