Grade 3 febrile neutropenia (not life-threatening)	Interrupt Everolimus until resolution of fever and neutropenia to grade $\leq 1$ . Hold further Everolimus until the ANC $\geq 1,500/\text{mm}^3$ and fever has resolved. Then resume Everolimus at the lower dose level. If febrile neutropenia recurs, discontinue Everolimus.
Grade 4 febrile neutropenia (life-threatening)	Discontinue Everolimus.
Any hematological or non-hematological toxicity requiring interruption for <math>\geq 3</math> weeks	Discontinue Everolimus.

\*Grade 3 hyperlipidemia (hypercholesterolemia and/or hypertriglyceridemia) should be managed using medical therapies (see Sec. 9.3.2).

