## Memorial Sloan-Kettering Cancer Center IRB Protocol

**IRB#: 08-123 A(8)**

**Table 7 Guidelines for management of hepatitis B**

HBV reactivation (with or without clinical signs and symptoms)*	
For patients with baseline results: Positive HBV-DNA OR positive HBsAg  reactivation is defined as: [Increase of 1 log in HBV-DNA relative to baseline HBV-DNA value OR new appearance of measurable HBV-DNA] AND ALT elevation x 5 ULN	Treat: Start a second antiviral AND Interrupt study drug administration until resolution: • $\leq$ grade 1 ALT (or baseline ALT, if $>$ grade 1) and • $\leq$ baseline HBV-DNA levels  If resolution occurs within <math>\leq</math> 28 days, study drug should be re-started at one dose level lower, if available. If the patient is already receiving the lowest dose of study drug according to the protocol, the patient should restart at the same dose after resolution. Both antiviral therapies should continue at least 4 weeks after last dose of study drug. If resolution occurs <math>></math> 28 days, patients should discontinue study drug but continue both antiviral therapies at least 4 weeks after last dose of study drug.
For patients with baseline results: Negative HBV-DNA and HBsAg AND [Positive HBs Ab (with no prior history of vaccination against HBV), OR positive Hbc Ab]  reactivation is defined as: New appearance of measurable HBV-DNA	Treat: Start first antiviral medication AND Interrupt study drug administration until resolution: • $\leq$ baseline HBV-DNA levels  If resolution occurs within <math>\leq</math> 28 days, study drug should be re-started at one dose level lower, if available. If the patient is already receiving the lowest dose of study drug according to the protocol, the patient should restart at the same dose after resolution. Antiviral therapy should continue at least 4 weeks after last dose of study drug. If resolution occurs <math>></math> 28 days, patients should discontinue study drug but continue antiviral therapy at least 4 weeks after last dose of study drug.

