\* All reactivations of hepatitis B are to be recorded as grade 3 (CTCAE v 3.0 Metabolic Laboratory/Other: Viral Re-activation), unless considered life threatening by the investigator; in which case they should be recorded as grade 4 (CTCAE v 3.0 Metabolic Laboratory/Other: Viral Re-activation). Date of viral reactivation is the date on which both DNA and ALT criteria were met (e.g. for a patient who was HBV-DNA positive on 01-JAN-10 and whose ALT reached  $\geq$  5  $\times$  ULN on 01-APR-10, the date of viral reactivation is 01-APR-10).

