## Memorial Sloan-Kettering Cancer Center IRB Protocol

IRB#: 08-123 A(8)

Footnotes for Schedule of Events	
1. Complete blood count (CBC) with differential and platelets	
2. Comprehensive panel (i.e. serum electrolytes including sodium, potassium, chloride, bicarbonate, phosphorus, calcium, glucose, blood urea nitrogen, creatinine, SGOT (AST), SGPT (ALT), alkaline phosphatase, total bilirubin, total protein, albumin, uric acid).	
Fasting Lipids include triglycerides, total cholesterol, HDL and LDL.	
3. Disease Assessment/Tumor Measurements: Re-staging imaging studies will be performed after every two cycles of treatment (1 cycle = 4 weeks) during the first five years of treatment and after study completion or withdrawal. Imaging studies should be performed during weeks 7 or 8. The same imaging studies performed at baseline (e.g., CT or MRI) should be performed throughout the study, when possible. Baseline chest CT or chest x-ray must be performed. If chest CT or chest x-ray is not part of the disease assessment, it must be repeated every 2 months. Bone x-ray(s)/scan to be performed if bone metastases are present.	
4. Adverse Events: Patients must be followed for adverse events from the first day of study treatment until at least 28 days after the last on-study treatment administration, or until all serious or study drug-related toxicities have resolved or are determined to be "chronic" or "stable," whichever is later. Serious adverse events should be monitored and reported as described in the protocol.	
5. Post-study survival status: Follow-up survival information will be collected for all patients by clinic visit or telephone contact approximately every 6 months for up to 2 years from the date of first dose of Everolimus. Patients will be followed until disease progression and/or death.	
6. Physical Examination/Hematology/Biochemistry/Fasting Lipids: Physical Examination/ Hematology/ Biochemistry/Fasting Lipids on Cycle 1 Day 1 is not required if performed within 7 days of Day 1 unless clinically indicated.	
7. Post Treatment/Withdrawal: This visit will take place 1 month after the last dose of study drug. Patients with ongoing study drug-related toxicities should be followed as dictated in footnote 4. These patients should be followed at the interval deemed appropriate by their study physician.	

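### For hepatitis B reactivation, Table 7 restarts Everolimus where Table 4 and Section 9.3 end it: holds of about 22 to 28 days, and grade 4 events

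*Combined protocol and SAP*

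**What the plan says.** Two section and table numbers are used twice in the protocol. Here, Section 9.3 means the part on monitoring suspected toxicities, and Table 7 means the hepatitis B management guidelines, not the Schedule of Events.

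- **Table 4, last row.** It covers "Any hematological or non-hematological toxicity requiring interruption for" three weeks or longer, and the action is to discontinue Everolimus.
- **Table 4, non-hematological grade 4 row.** The action is to discontinue Everolimus, whatever the duration.
- **Section 9.3.** The trigger is worded "If a patient requires a dose delay of > 21 days from the intended day of the next scheduled dose". The consequence is mandatory and reaches beyond the drug: "then the patient must be discontinued from the study".
- **Table 7.** Drug is interrupted at reactivation. If resolution comes within 28 days, "study drug should be re-started at one dose level lower, if available"; a patient already at the lowest level restarts at the same dose. Beyond 28 days, in the baseline group with positive HBV-DNA or HBsAg, "patients should discontinue study drug but continue both antiviral therapies at least 4 weeks after last dose of study drug". The other baseline group has the same 28-day limit.
- **Table 7 footnote.** "All reactivations of hepatitis B are to be recorded as grade 3", or as grade 4 if the investigator considers them life-threatening.

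**The concern.** The footnote to Table 7 makes every reactivation a graded CTCAE event. On its face, each one is then a non-hematological toxicity within Table 4, and each hold is a dose delay within Section 9.3. Neither place exempts hepatitis B, and Table 7 does not say that it displaces them.

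What is at stake is whether a patient is re-exposed to study drug after a serious hepatic event. Two investigators reading the same protocol could act in opposite ways, and each could point to a passage in support. The consequences also differ in kind: Table 4 ends the drug, whereas Section 9.3 ends participation in the study.

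**Working it through.** The plan states no figure to reproduce. The check sets the rules side by side.

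**1. Interruption length.** Inputs: Table 4 stops drug if d ≥ 21 days; Section 9.3 removes the patient if d > 21; Table 7 restarts if d ≤ 28 and stops if d > 28.

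| Days to resolution (d) | Table 4, last row | Section 9.3 | Table 7 |
|---|---|---|---|
| up to 20 | limit not reached | limit not reached | restart |
| 21 | stop drug | limit not reached | restart |
| 22 to 28 | stop drug | off study | restart |
| 29 or more | stop drug | off study | stop drug |

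Table 7 opposes both other rules on days 22 to 28 (28 − 22 + 1 = 7 day values). It opposes Table 4 on days 21 to 28 (8 day values).

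**2. Sensitivity to the clocks.** The three rules count different things: length of interruption, delay from the intended next dose, and time to resolution. Assume that interruption and resolution are both counted from the last dose taken. With daily dosing, the delay is then d − 1, so Section 9.3 acts when d > 22 and its conflict with Table 7 runs over days 23 to 28 (6 day values). At the lowest level in Table 3 (alternate-day dosing), the delay is d − 2 and the conflict runs over days 24 to 28 (5 day values). The window moves by a day or two but does not close.

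**3. Grade.** For a reactivation recorded as grade 4, Table 4's grade 4 row discontinues Everolimus. Table 7 makes no distinction by grade and directs a restart if resolution comes within 28 days. This conflict does not depend on the length of the hold: it is present at day 10 as much as at day 25.

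**4. Exemptions.** Table 4 does hand some events to other rules. Its grade 3 row reads "Grade 3 (except hyperlipidemia*)(except pneumonitis", with pneumonitis sent to Table 5 and grade 3 hyperlipidemia to Section 9.3.2. Hepatitis B is not handled in this way, and the last row of Table 4 carries no exception at all. The hepatitis B rules are Section 9.3.4, so they sit under the same Section 9.3 that contains the 21-day rule.

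**The case against.** The strongest reply is that the specific rule governs the general one. Table 4 is captioned for suspected Everolimus toxicity, and Section 11.0 describes its content as general recommendations. Table 7 is dedicated to hepatitis B, and the text before it shows that it came in by amendment. This is a plausible reading against Table 4. It is still only an inference: the dose-modification text says that interruptions for unacceptable toxicity follow the rules in Table 4, and no precedence is written down. Nor does it answer Section 9.3, whose requirement is mandatory and covers any dose delay.

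The event is also likely to be rare. Section 11.0 calls reactivation with everolimus sporadic, the exclusion criteria remove chronic active and chronic persistent hepatitis, and Table 6 provides for prophylaxis and HBV-DNA monitoring. That stands, and it limits the size of the point.

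Two stronger readings are tempting, and the documents do not support either.

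- **Table 4 and Section 9.3 contradict each other at exactly 21 days.** They do not. On that day Table 4 stops the drug and Section 9.3 requires nothing, so both can be followed.
- **Removal from the study costs two-month assessments, and so power.** Section 14.0 rests on progression-free status at two months, and footnote 3 of the Schedule of Events says "Imaging studies should be performed during weeks 7 or 8". A hold from about week 4 would reach its limit at about that time. But the treatment plan keeps imaging at regular intervals when cycles are delayed. Footnote 3 also requires imaging at withdrawal, and footnote 7 places that visit one month after the last dose, near week 8 in this example. Footnote 5 follows patients to progression or death. Section 12.4.5 does not count stopping drug as an event, and Section 14.0 does not make a patient inevaluable for stopping because of a drug-related event. A hold from about week 2 would put the withdrawal visit near week 6, before the scan, but any early stop for toxicity does that; the conflict between limits does not create it. A power loss calculated from missing scans would follow from any unreplaced missing data and would not measure this defect.

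**Conclusion.** The point holds as an internal contradiction in clinical instructions. For hepatitis B reactivation, Table 7 directs a restart where Section 9.3 removes the patient from the study (about days 22 to 28) and where Table 4 stops the drug (from day 21, and for grade 4 events whatever the duration). This rests on treating a reactivation graded under CTCAE as a toxicity within Table 4. The conflict with Section 9.3 does not need that assumption.

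The number of patients affected is not given and is probably small. No effect on the primary endpoint, on power or on the trial's conclusion is shown. The reason to act is that the protocol gives opposite directions on re-exposure after a serious hepatic event, and that this is cheap to remove.

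**What to change.** Reconcile the last row and the grade 4 row of Table 4, the dose-delay rule in Section 9.3, and Table 7 with its footnote, so that exactly one instruction applies to each hepatitis B reactivation. In particular:

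- state which passage governs the length of interruption, and from which day it is counted;
- state which passage governs a reactivation recorded as grade 4;
- if Table 7 is meant to take precedence, write the exemption into Table 4 and Section 9.3, as Table 4 already does for pneumonitis; if it is not, amend Table 7;
- use consistent wording for stopping the drug and for leaving the study.

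The clinical team must choose the limit and the rule for grade 4 events; this review does not propose either. The cost is a wording amendment with its usual review, and no change to sample size, analysis or visit schedule.

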#### 9.3.1 Management of stomatitis/oral mucositis/mouth ulcers

Stomatitis/oral mucositis/mouth ulcers due to Everolimus should be treated using local supportive care.

When described, the disorder has been identified as inflammation or ulcers in the mouth. If exam reveals mouth ulcers, rather than a more general inflammation of the mouth, please classify the adverse event as 'mouth ulcers.' If inflammation is limited to the mouth without ulcers, please use the term 'stomatitis' rather than the less specific term 'mucositis.'

If the disorder appears elsewhere other than the mouth, please describe the location as well as any specific procedures carried out for exploration (e.g. endoscopy).

Please use the Grading according to the NIH-NCI Common Terminology Criteria for Adverse Events, Version 3.0 (CTCAEv3.0; <http://ctep.cancer.gov/forms/CTCAEv3.pdf>).

- Grade 1: minimal symptoms; normal diet
- Grade 2: symptomatic but can eat and swallow modified diet
- Grade 3: symptomatic and unable to adequately aliment or hydrate orally
- Grade 4: symptoms associated with life-threatening consequences

#### Recommendations:

1. For mild toxicity (Grade 1), use conservative measures such as non-alcoholic mouthwash or salt water (0.9%) mouthwash several times a day until resolution.
2. For more severe toxicity (Grade 2 or 3), the suggested treatments are topical analgesic mouth treatments (i.e., local anesthetics such as benzocaine, butyl aminobenzoate, tetracaine hydrochloride, menthol, or phenol) with or without topical corticosteroids, such as triamcinolone oral paste 0.1% (e.g. Kenalog in Orabase®).
3. Agents containing hydrogen peroxide, iodine, and thyme derivatives may tend to worsen mouth ulcers. It is preferable to avoid these agents.

Antifungal agents must be avoided unless a fungal infection is diagnosed. In particular, systemic imidazole antifungal agents (ketoconazole, fluconazole, itraconazole, etc.) should be avoided in all patients due to their strong inhibition of Everolimus metabolism (which leads to higher Everolimus exposures). Therefore, topical antifungal agents are preferred if an infection is diagnosed. Similarly, antiviral agents such as acyclovir should be avoided unless a viral infection is diagnosed.

## Memorial Sloan-Kettering Cancer Center IRB Protocol

IRB#: 08-123 A(8)

### 9.3.2 Management of hyperlipidemia and hyperglycemia

Treatment of hyperlipidemia should take into account the pre-treatment status and dietary habits. Blood tests to monitor hyperlipidemia must be taken in the fasting state. Grade 2 or higher hypercholesterolemia ( $>300$  mg/dL or  $7.75$  mmol/L) or grade 2 or higher hypertriglyceridemia ( $>2.5$  x upper normal limit) should be treated with a statin or appropriate lipid-lowering medication in addition to diet. Patients should be monitored clinically and through serum biochemistry for the development of rhabdomyolysis and other adverse events as required in the product label/data sheets for HMG-CoA reductase inhibitors. Patients who develop grade 4 hyperglycemia or grade 4 hyperlipidemia will be withdrawn from study.

Note: Concomitant therapy with fibrates and an HMG-CoA reductase inhibitor is associated with an increased risk of a rare but serious skeletal muscle toxicity manifested by rhabdomyolysis, markedly elevated creatine kinase (CPK) levels and myoglobinuria, acute renal failure, and sometimes death. The risk versus benefit of using this therapy should be determined for individual patients based on their risk of cardiovascular complications of hyperlipidemia.

Grade 3 hyperglycemia has been observed in patients receiving Everolimus therapy. In many cases in [Study Everolimus C2222] the affected patients had an abnormal fasting glucose at baseline. Based on this finding, optimal glucose control (indicated by fasting triglycerides  $\leq 2.5$  x ULN) must be achieved before starting a patient on Everolimus. Study patients should have their glucose levels monitored during Everolimus therapy.

### 9.3.3 Management of non-infectious pneumonitis

Both asymptomatic radiological changes (grade 1) and symptomatic non-infectious pneumonitis (grade 2 = not interfering with activities of daily living or grade 3 = interfering with activities of daily living and oxygen indicated) have been noted in patients receiving Everolimus therapy. Non-infectious pneumonitis has been associated with Everolimus and other mTOR inhibitors (Atkins 2004). All patients are required to undergo baseline/pretreatment pulmonary function tests and will be excluded from study treatment if TLC  $<50\%$  predicted, FVC  $<50\%$  predicted, or DLCO  $<40\%$  predicted. In order to monitor for asymptomatic (grade 1) non-infectious pneumonitis during study treatment, a chest CT scan or chest x-ray is required in addition to the monthly radiological tumor examinations. Additional chest CT scans may be performed when clinically necessary. If non-infectious pneumonitis develops, a consultation with a pulmonologist should be considered. If the patient develops grade 3 pneumonitis, treatment with Everolimus should be interrupted and the patient should be treated as medically indicated (short course corticosteroids, oxygen, etc).

Management of non-infectious pneumonitis suspected to be associated with Everolimus and dose modification instructions are provided in Table 5.

The attribution of changes on interval chest imaging will be recorded as related, possibly related, or unrelated to study drug.

## Memorial Sloan-Kettering Cancer Center IRB Protocol

IRB#: 08-123 A(8)

**Table 5 Management of non-infectious pneumonitis**

Worst Grade Pneumonitis	Required Investigations	Management of Pneumonitis	Everolimus Dose Adjustment
Grade 1	CT scans with lung windows and pulmonary function testing including: spirometry, DLCO, and room air O 2 saturation at rest. Repeat chest x-ray/CT scan every 2 Cycles until return to baseline.	No specific therapy is required.	Administer 100% of Everolimus dose.
Grade 2	CT scan with lung windows and pulmonary function testing including: spirometry, DLCO, and room air O 2 saturation at rest. Repeat each subsequent Cycle until return to baseline. Consider bronchoscopy. *	Symptomatic only. Prescribe corticosteroids if cough is troublesome.	Reduce Everolimus dose until recovery to ≤ Grade 1. Everolimus may also be interrupted if symptoms are troublesome. Patients will be withdrawn from the study if they fail to recover to ≤ Grade 1 within 3 weeks.
Grade 3	CT scan with lung windows and pulmonary function testing including: spirometry, DLCO, and room air O 2 saturation at rest.; Repeat each subsequent Cycle until return to baseline. Bronchoscopy is recommended. *	Prescribe corticosteroids if infective origin is ruled out. Taper as medically indicated.	Hold treatment until recovery to ≤ Grade 1. May restart protocol treatment within 3 weeks at a reduced dose (by one level) if evidence of clinical benefit. Patients will be withdrawn from the study if they fail to recover to ≤ Grade 1 within 3 weeks.
Grade 4	CT scan with lung windows and required pulmonary function testing includes: spirometry, DLCO, and room air O 2 saturation at rest. Repeat each subsequent Cycle until return to baseline. Bronchoscopy is recommended. *	Prescribe corticosteroids if infective origin is ruled out. Taper as medically indicated.	Discontinue treatment.

\*A bronchoscopy with biopsy and/or bronchoalveolar lavage is recommended.

